3. BACKGROUND

a. Past Experimental and/or Clinical Findings

Less than 1 out of every 4 adolescents with type 1 diabetes (T1D) meets the American Diabetes Association (ADA) guidelines for target hemoglobin A1c, a common indicator of glycemic control. These deteriorations in glycemic control during adolescence can persist into adulthood. Family-based interventions are empirically supported to offset this adolescent risk, although behavioral health services are rarely included in diabetes care. Despite the ADA recommendation for integrated care, a minority of diabetes clinics offer any behavioral health services and less than 1 in 5 include a psychologist. Lack of behavioral health providers who specialize in diabetes as well as institutional/economic constraints serve as barriers toward more integrated models of care, enhancing the need for intervention options that require limited resources. The current study seeks to address that need by evaluating an evidence-based family intervention to be optimized and integrated within real-world clinic care for adolescents with T1D and their parents.

b. Findings from Past Animal Experiments

None.

4. PARTICIPANT POPULATION

a. Planned Enrollment

5/11/21 Page 3 of 11

The target enrollment will be 165 families (165 adolescents and 165 caregivers). Potential participants will be recruited through the Division of Pediatric Endocrinology and Diabetes at Stanford, the Stanford Diabetes Research Center's clinical registry, and online email listerys. Inclusion criteria are: 1) T1D diagnosis according to ADA criteria for at least 6 months, 2) ages 12-19, and 3) participation of at least one cohabitating parent/caregiver. The age range was chosen due to evidence that diabetes management problems first arise between the ages of 11 and 18 years. Exclusion criteria will be lack of access to a smartphone or Wi-Fi via computer, restricted English proficiency, and pervasive developmental, data collection or intervention modules.

Glucose monitoring data will be collected via glucose monitors that are already in use, among participants already using these devices at the time of enrollment, with data being shared by the participant with the research team via secure online portals created and run by their corresponding device company. For participants who are not already using glucose monitors at the time of enrollment, Libre 2 glucose monitor devices will be provided by study staff, including training on use and support throughout use, and will be born to collect 2 weeks of data at each time point.

b. Age, Gender, and Ethnic Background

Adolescents ages 12-19 and at least one caregiver will be recruited to participate across genders and ethnic backgrounds.

c. Vulnerable Populations

165 adolescents will be enrolled. Normative adolescent shifts in cognitive and affective development and transitions from parental dependence toward greater autonomy can compromise self-management and glycemic control among adolescents with T1D. Less than 1 out of every 4 adolescents with type 1 diabetes (T1D) meets the American Diabetes Association (ADA) guidelines for target hemoglobin A1c, a common indicator of glycemic control. These deteriorations in glycemic control during adolescence can persist into adulthood. Family-based interventions are empirically supported to offset this adolescent risk, although behavioral health services are rarely included in diabetes care. The current study seeks to identify ways to offset risks among adolescents.

d. Rationale for Exclusion of Certain Populations

Women, minorities, and children will be included.

e. Stanford Populations

None.

f. Healthy Volunteers

None.

g. Recruitment Details

5/11/21 Page 4 of 11

Potential participants will be recruited through the Stanford Pediatric outpatient diabetes clinics of the Division of Pediatric Endocrinology and Diabetes at Stanford, the Stanford Diabetes Research Center's clinical registry and similar IRB approved email lists compromised of individuals who requested to be contacted about potential research participation, as well as online email listerys, and social media.

In-clinic recruitment will consist of posting flyers in clinic, including exam rooms, waiting room, and hallways. The research team will recruit with the flyers and provide assistance with completing the online screening and informed consent when possible. Clinic staff will also be provided with copies of the flyers to distribute to potential participants. Stanford pediatric diabetes clinics are a common venue for research and patients are made aware that they participation or decision not to participate in research will in no way compromise the services they receive there and that participation can be withdrawn at any time without any penalty or negative impact to the services that they receive.

Potential participants will also be contacted through our endocrine and IRB approved patient recruitment lists, including the Stanford Diabetes Research Center's clinical registry (in which subjects have already consented to be recruited for research studies). Stanford Diabetes Research Center's clinical registry is compromised of individuals who have expressed interest in participating in research and have voluntarily included their name in the registry to be contacted for potential participation in studies. More information on the SDRC registry can be found at: https://sdrc.stanford.edu/clinical-research-registry. Participants will also be recruited through online flyers sent out through established diabetes-related listerys run by diabetes organizations. If/when eligibility criteria are revised, a re-send recruitment email (see Section 16) will be sent to again across listerys to clarify that interested potential participants who were previously ineligible have an opportunity to complete the screening again as they may now be eligible.

The IRB-approved recruitment flyer and email will also be circulated through online websites, forums newsletters, emails listervs, and social media pages (primarily run by diabetes organizations such as DYF and JDRF) and shared with diabetes providers and clinics within and outside of Stanford. These online avenues are often used to disseminate information to families of youth with type 1 diabetes offering various information and resources, including opportunities to participate in studies similar to the current study.

h. Eligibility Criteria

i. Inclusion Criteria

Inclusion criteria are: 1) type 1 diabetes (T1D) diagnosis according to ADA criteria for at least 6 months, 2) ages 12-19, and 3) participation of at least one cohabitating parent/caregiver. The age range was chosen due to evidence that diabetes management problems first arise between the ages of 11 and 18 years.

ii. Exclusion Criteria

Exclusion criteria will be lack of access to a smartphone or Wi-Fi via computer, restricted English proficiency, and pervasive developmental, cognitive, or psychiatric limitations that compromise participation in the intervention sessions and study. Glucose monitors will be provided to

5/11/21 Page 5 of 11

participants who are not already using these devices such that device use will not be a criterion of eligibility or exclusion.

i. Screening Procedures

Eligibility will be determined based on a screening survey completed through RedCap prior to informed consent and enrollment.

j. Participation in Multiple Protocols

Both verbal and written information on consent (and assent) will be obtained by the research staff and/or PI to assess understanding of consent during interactions with potential participants. Individuals who are not proficient in English or have any impairment in communication that might compromise informed consent/assent will be excluded from the study.

k. Payments to Participants

We will enroll 330 participants (165 adolescents with type 1 diabetes and their 165 caregivers). Participants will be asked to participate in a 6-session family-based intervention delivered via the internet, complete online surveys, provide glucose monitoring data either via continuous glucose monitors (CGMs) that the have already been using prior to enrollment or blinded CGMs provided by the study, and provide A1C test results that will be collected via chart review or from participants sharing their test results at baseline, 6-month, and 12-month follow-up. We will compensate each parent and each adolescent participant with a total of \$\frac{1}{2}\$ worth of gift cards for complete data collection. Graduated incentives are provided at each time point:

\square Baseline = \$
\Box First intermediate survey = \$
\square Second intermediate survey = \$
\Box Third intermediate survey = \$
\square 3-month follow-up = \$
\Box 6-month follow-up = \$
□ 12-month follow-up = \$

l. Costs to Participants

None.

m. Planned Duration of the Study

The probable duration of the entire study is 4.5 years. We anticipate screening will require 5 minutes, recruitment of all 165 participants can take up to 3 years, and activate participation in the study will require approximately 12 months. Each participant will spend 8 hours total on study participation and analysis of participant data will require approximately 1 year. Surveys will require approximately 30 minutes each to complete and each intervention sessions for the intervention group will require approximately 10-20 minutes each.

5. RISKS

a. Potential Risks

Investigational devices

5/11/21 Page 6 of 11

None.

ii. Investigational drugs

None.

iii. Commercially available drugs, biologics, reagents or chemicals

None.

iv. Procedures

Data Collection: Self-reported survey will be kept confidential and collected online via secure REDCap database system. There are no known psychological risks to subjects completing self-report subjective rating scales or participating in the intervention sessions. However, the survey and intervention may contain items or questions that make the subjects feel uncomfortable in that they ask about their physical and psychological health and feelings/emotions. Subjects will be informed that any items on questionnaires or topics discussed in the intervention modules that produce these effects may be skipped or ignored. Further, [name] (PI) is a licensed psychologist who will be available to participants to address any potential discomfort or risks that may arise, assess, and triage as appropriate. If any discomfort or adverse events arise with continuous glucose monitor use, our research staff including [name] will be available to assist and assure that the appropriate medical services are received to address the issue, as well as minimize risk in general.

Intervention: Engaging in the intervention modules carries minimal risk for emotional discomfort or stress. Subjects will have the option of not participating in conversations or exercises in the intervention modules that cause them any discomfort. They will also be free to withdraw from participating in the intervention and/or overall study at any time. All intervention modules will be carried out by [name], a licensed clinical psychologist (license #29814) or a clinically trained interventionist who will be trained and supervised by [name]. Adolescent and caregiver participants will be advised of their rights to withdraw from the intervention at any time without penalty or consequence on their receipt of future health care services at Stanford University's Lucile Packard Children's Hospital of affiliated clinics.

Protections Against Risk. [name] and all research staff have completed rigorous training in the protection of human subjects, including CITI training. The plan for protecting privacy and confidentiality recognizes that the protection of privacy in studies involving sensitive data is of utmost importance. We will attempt to do this in several ways. The PI will introduce the study to eligible participants and explain the purposes, benefits, and risks of the project to the subjects, and offer them an opportunity to ask questions and/or decline participation. The voluntary and confidential nature of the research, as well as limits to confidentiality, will be highlighted during informed consent process. Study participation will not interfere with clinical care and all patients have standard access to the treatment team on a routine (clinical care) and emergency basis. All responses to interview items will be given by subjects in private. Survey data collection will only occur through tools and resources that have acceptable security features. We will minimize all communications that involve names or other identifying information. All clinically-relevant and study information will be kept in locked files in locked offices or password protected files. Our research staff including [name] will be available to assist and assure that the appropriate medical services are received to address any issues with glucose monitoring, as well as minimize risk of issues related to device use.

The participants will send the A1c test kits with their samples to the Advanced Research and Diagnostic Laboratory (ARDL) at the University of Minnesota where it will be processed and the results will be sent securely without any identifiers to the study team.

5/11/21 Page 7 of 11

All recordings of intervention sessions will be saved on a password-protected secure server. Information about subjects will not be accessible to any nonauthorized study personnel without the written consent of the subject. In all datasets we will use ID numbers only. A separate dataset linking names with ID numbers will be accessible only to authorized study personnel under the direction of the PI.

v. Radioisotopes/radiation-producing machines

None.

vi. Physical well-being

None.

vii. Psychological well-being

Data Collection: Self-reported survey will be kept confidential and collected online via secure REDCap database system. There are no known psychological risks to subjects completing self-report subjective rating scales or participating in intervention sessions. However, the surveys and intervention topics may contain items or questions that make the subjects feel uncomfortable in that they ask about their physical and psychological health and feelings/emotions. Subjects will be informed that any items on questionnaires or topics discussed in the intervention modules that produce these effects may be skipped or ignored. Further, [name] (PI) is a licensed psychologist who will be available to participants during data collection and will be facilitated the intervention in order to address any potential discomfort or risks that may arise, assess, and triage as appropriate.

Intervention: Engaging in the intervention modules carries minimal risk for emotional discomfort or stress. Subjects will have the option of not participating in conversations or exercises in the intervention modules that cause them any discomfort. They will also be free to withdraw from participating in the intervention and/or overall study at any time. All intervention modules will be carried out by [name], a licensed clinical psychologist (license #29814). Adolescent and caregiver participants will be advised of their rights to withdraw from the intervention at any time without penalty or consequence on their receipt of future health care services at Stanford University's Lucile Packard Children's Hospital of affiliated clinics. Protections Against Risk. [name] has completed and will maintain rigorous training in the protection of human subjects, including CITI training. The plan for protecting privacy and confidentiality recognizes that the protection of privacy in studies involving sensitive data is of utmost importance. We will attempt to do this in several ways. The PI will introduce the study to eligible participants and explain the purposes, benefits, and risks of the project to the subjects, and offer them an opportunity to ask questions and/or decline participation. The voluntary and confidential nature of the research, as well as limits to confidentiality, will be highlighted during informed consent process. Study participation will not interfere with clinical care and all patients have standard access to the treatment team on a routine (clinical care) and emergency basis. All responses to interview items will be given by subjects in private. Survey data collection will only occur through tools and resources that have acceptable security features. We will minimize all communications that involve names or other identifying information. All clinically-relevant and study information will be kept in locked files in locked offices or password protected files.

All recordings of intervention sessions will be saved on a password-protected secure server. Information about subjects will not be accessible to any nonauthorized study personnel without the written consent of the subject. In all datasets we will use ID numbers only. A separate dataset linking names with ID numbers will be accessible only to authorized study personnel under the direction of the PI.

5/11/21 Page 8 of 11

viii. Economic well-being

None.

ix. Social well-being

None.

x. Overall evaluation of risk

NA.

b. International Research Risk Procedures

NA.

c. Procedures to Minimize Risk

Protections Against Risk. [name] and all research staff have completed and will maintain rigorous training in the protection of human subjects, including CITI training. The plan for protecting privacy and confidentiality recognizes that the protection of privacy in studies involving sensitive data is of utmost importance. We will attempt to do this in several ways. Research staff will introduce the study to eligible participants and explain the purposes, benefits, and risks of the project to the subjects, and offer them an opportunity to ask questions and/or decline participation. The voluntary and confidential nature of the research, as well as limits to confidentiality, will be highlighted during informed consent process. Study participation will not interfere with clinical care and all patients have standard access to the treatment team on a routine (clinical care) and emergency basis. All responses to interview items will be given by subjects in private. Survey data collection will only occur through tools and resources that have acceptable security features. We will minimize all communications that involve names or other identifying information. All clinically-relevant and study information will be kept in locked files in locked offices or password protected files.

All recordings of intervention sessions will be saved on a password-protected secure server. Information about subjects will not be accessible to any nonauthorized study personnel without the written consent of the subject. In all datasets we will use ID numbers only. A separate dataset linking names with ID numbers will be accessible only to authorized study personnel under the direction of the PI.

d. Study Conclusion

The study will end after 4.5 years. Participation will end one year after baseline data collection completion. No adverse events are anticipated.

e. Data Safety Monitoring Plan (DSMC)

i. Data and/or events subject to review

We will review CGM data for wide and dangerous fluctuations in glucose levels, and report to the study participant and clinical team (if acceptable to study participant).

ii. Person(s) responsible for Data and Safety Monitoring

[name] is responsible for ongoing monitoring and [name] will serve as Safety Monitor.

5/11/21 Page 9 of 11

iii. Frequency of DSMB meetings

During the course of the trial, data will be reviewed monthly for completeness and accuracy (all data points fall within the possible range for each measure), with guidance from the mentorship team. In addition, bi-weekly reviews will examine occurrence of adverse events and whether participants are satisfied with their participation.

Because this study involves randomization and interventions associated with diabetes management, but because the study itself is not masked and is low risk, the PI will be involved with the oversight in conjunction with an external Safety Monitor (rather than a Data Safety and Monitoring Board). The Safety Monitor will be informed of all serious adverse events and any unanticipated adverse device events that occur during the study and will review compiled adverse event data at the completion of the study.

iv. Specific triggers or stopping rules

The PI will be responsible for evaluating each unanticipated problem and determining whether it affects the risk/benefit ratio of the study and whether modifications to the protocol and consent forms are required. Specific triggers include any indication through data collection or participant interactions that indicate severe risk, such as indications of diabetic ketoacidosis or suicidality. These issues are rare but our team will be trained in identifying early signs to immediately inform PI to determine whether reporting, stopping, and/or other actions must be taken.

v. DSMB Reporting

The PI will be responsible for reporting unexpected problematic events involving any aspect of the study to the NIH and local IRB per institutional guidelines. The Safety Monitor will be informed of all serious adverse events and any unanticipated adverse device events that occur during the study and will review compiled adverse event data at the completion of the study. Unanticipated problems to be assessed include adverse events, deviations from the study protocol, problems with informed consent, and confidentiality violations.

vi. Will the Protocol Director be the only monitoring entity? (No)

[name] (PI) will primarily be responsible for monitoring though the project research coordinator will be trained in monitoring and [name] will be consulted as needed.

vii. Will a board, committee, or safety monitor be responsible for study monitoring? (No)

The Safety Monitor will be involved, as needed, in monitoring but will not be responsible for monitoring.

f. Risks to Special Populations

Benefits a) Describe the potential benefit(s) to be gained by the participants or by the acquisition of important knowledge which may benefit future participants, etc. This study presents no greater than minimal risk, given that all the procedures are no more invasive or risky than standard

5/11/21 Page 10 of 11

practices within diabetes management. Further, research staff will be available to prevent, address, and resolve any potential risks that may arise.

6. BENEFITS

The potential benefit of this study is the provision of new knowledge and skills about methods of improving glycemic control among adolescents with type 1 diabetes. Participants may find intervention sessions interesting and relevant.

Collection of the psychosocial and clinical data may provide information for diabetes clinicians and other stakeholders to help optimize the way that new beneficial technology is introduced to their patients.

7. PRIVACY AND CONFIDENTIALITY

All participant information and specimens are handled in compliance with the Health Insurance Portability and Accountability Act (HIPAA) and privacy policies of Stanford University, Stanford Health Care, and Stanford Children's Health.

5/11/21 Page 11 of 11

Insul-In This Together Program: Optimizing Family-based Interventions for Adolescents With Type 1 Diabetes and Their Parents

Statistical Analysis Plan

NCT04589689

[figure not shown]
May 11, 2021

Statistical Analysis Plan

[figure not shown]
1. Planned sample size was 150 enrolled parent-adolescent dyads. The final sample included 157 parent-adolescent dyads.
2. Basic two-sided t-tests for primary and secondary outcomes using a p-value cutoff of <.05. Compared participants based on condition assignments: intervention versus waitlisted control.
3. Simple regression models: test main effects on outcomes at 3-month and 6-month follow-ups (in Mplus)
 - a. Covariates: Teen age, diabetes duration, baseline TIR, baseline QOL, and baseline outcome (if other than TIR or QOL)
 - b. Auxiliary variables (to inform data imputation, but not directly included in model): Teen gender, baseline A1c, Teen PAID, and Parent PAID
4. Moderation analyses: separate regression models for each outcome that include set of covariates and an interaction term of condition x moderator.
 - a. Covariates: age, diabetes duration, baseline QOL, and baseline TIR
 - b. Outcomes: QOL, TIR, A1c, Teen PAID, and Parent Paid
 - c. Moderators (at baseline):
 1. Closed loop
 2. A1c \leq 7.5%
 3. TIR \geq 70%
 4. Race/ethnicity
 5. Income
 6. Insurance
 7. Baseline level of corresponding outcome
5. Mediation analyses: single mediator models
 - a. Mediator: immediate posttest
 - b. Outcomes: 3-month and 6-month follow-ups
6. 12-month follow-up – combine both conditions and look through 6-months (but for control the 6-month value 12-month value)

Regression Model

6-Month Follow-Up

Moderation Models

Single Mediator Model

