Glucose monitoring data will be collected via glucose monitors that are already in use, among participants already using these devices at the time of enrollment, with data being shared by the participant with the research team via secure online portals created and run by their corresponding device company. For participants who are not already using glucose monitors at the time of enrollment, Libre 2 glucose monitor devices will be provided by study staff, as well as training on use following FDA-approved self-start guides that are available online. Research staff will also provide support throughout use, and will be used to collect 2 weeks of data at each time point. A smaller set of surveys will also be conducted at approximately 2-, 4-, and 6-week follow-ups (after every 2 sessions for the intervention group and at corresponding time points for the control group). Participants will be asked to report their A1Cs (or gathered from medical records) at baseline and 6-month and 12-month follow-ups. If participants do not have an A1c result from the target period, they will be sent via mail a blood collection kit that can be completed at home and returned via mail to a laboratory where the specimen will be tested for HbA1c.

b. Procedure Risks

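### The moderation models drop the baseline-outcome covariate used in the main-effect models, which costs precision in 18 of 35 interaction tests

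*SAP*

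**What the plan says.** SAP item 3a sets the main-effect adjustment: "Covariates: Teen age, diabetes duration, baseline TIR, baseline QOL, and baseline outcome (if other than TIR or QOL" (closing bracket omitted). Item 3b adds variables that support the handling of missing data only: "Auxiliary variables (to inform data imputation, but not directly included in model): Teen gender, baseline A1c, Teen PAID, and Parent PAID".

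Item 4 then describes the moderation analyses as "separate regression models for each outcome that include set of covariates and an interaction term of condition x moderator". Item 4a gives its own list: "Covariates: age, diabetes duration, baseline QOL, and baseline TIR". Item 4b names five outcomes: "Outcomes: QOL, TIR, A1c, Teen PAID, and Parent Paid". Item 4c names seven baseline moderators. The second is A1c cut at 7.5%, and the seventh is "Baseline level of corresponding outcome". Item 4 names no time point, no auxiliary variables and no main effects for condition or moderator.

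**The concern.** Set side by side, the two lists differ in one respect. Age, diabetes duration, baseline TIR and baseline QOL are in both, and the baseline outcome is only in item 3a. For QOL and TIR this makes no difference, because item 4a already contains their baselines. A1c, Teen PAID and Parent PAID lose theirs except under moderator 7, where it enters as the moderator itself.

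The data are available, since items 3b and 4c both rely on these baselines. Item 3b does not fill the gap: an auxiliary variable informs the imputation but does not remove baseline variation from the interaction estimate.

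Because allocation is randomised, the omission does not bias the interaction or inflate its error rate. What is at stake is precision, in the models that have least of it to spare.

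**Working it through.** The plan states no number of moderation models and no power figure for them, so there is no figure of its own to reproduce.

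**Count at 6 months.** Assume one model per outcome–moderator pair, moderator main effects fitted, and moderator 7 continuous.
- All models: 5 × 7 = 35.
- QOL and TIR, own baseline in item 4a: 2 × 7 = 14.
- A1c, Teen PAID, Parent PAID under moderator 7: 3 × 1 = 3.
- Without the continuous baseline outcome: 35 − 14 − 3 = 18.

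One of the 18, A1c as outcome with A1c ≤ 7.5% as moderator, holds a yes/no version; the other 17 hold none. Read literally, with no moderator main effects, the count is 21.

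**Count at 3 months, if those models are run.** Protocol section 2.a gives the A1c schedule: "Participants will be asked to report their A1Cs (or gathered from medical records) at baseline and 6-month and 12-month follow-ups". Section 4.k lists the same times. With no 3-month A1c there are 4 × 7 = 28 models, of which 2 × 6 = 12 lack the term.

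**Why precision is scarce.** SAP item 1 states: "The final sample included 157 parent-adolescent dyads". With 1:1 arms, a 50/50 moderator and residual SD 1, SE(main effect) = √(4/157) = 0.160 and SE(interaction) = √(16/157) = 0.319, a ratio of 2.

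**Gain from adding the term.** Let r be the partial correlation of baseline with follow-up outcome, given the covariates already listed. Then

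SE reduction = 1 − √[(1 − R² with)/(1 − R² without)] = 1 − √(1 − r²).

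| r | 0.25 | 0.4 | 0.5 | 0.6 | 0.68 |
|---|---|---|---|---|---|
| SE reduction | 3% | 8% | 13% | 20% | 27% |

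The documents give no correlations. Those below are assumptions in absolute value, with age and duration taken as unrelated to the outcome.

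- *PAID, low end.* Baseline with follow-up 0.5, QOL with follow-up 0.5, QOL with baseline PAID 0.7, TIR with everything 0.2. R² rises from 0.260 to 0.301, so the reduction is 1 − √(0.699/0.740) = 2.8%.
- *PAID, high end.* Baseline with follow-up 0.7, QOL and TIR with follow-up 0.4, predictors 0.2 with each other. R² rises from 0.267 to 0.611, a reduction of 27.1%.
- *A1c.* Baseline with follow-up 0.6–0.7, TIR with baseline A1c 0.6–0.7, TIR with follow-up 0.4–0.5, QOL with each 0.2–0.3. Each was varied separately in steps of 0.05. Of 729 combinations, 440 were kept; those in which an adjusted coefficient changed sign were dropped. Low end: R² from 0.292 to 0.389, reduction 7.1%. High end: R² from 0.232 to 0.517, reduction 20.6% (from unrounded R²).
- *A1c by A1c ≤ 7.5%.* On the same 440 combinations with normal baseline A1c: 4.0–11.5% at a 50/50 split and 5.0–14.4% at 20/80.

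**Cost of the term.** With 157 families, complete data and a one-parameter moderator, the model has 8 parameters: intercept, condition, moderator, interaction and four covariates. That leaves 149 degrees of freedom, or 148 with the term. If the baseline adds nothing, the SE grows by √(149/148) − 1 = 0.34%. Break-even is r = √(1/149) = 0.08.

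**Simulation.** n = 157, 3,000 runs in each of 20 settings, main effects fitted. The settings took the low and high ends above, with the moderator split 50/50 or 20/80, and either unrelated to baseline, correlated 0.3 with it, or a cut of baseline A1c. Mean SE fell by 2.4–26.8% (PAID), 6.6–20.4% (A1c) and 3.7–14.4% (A1c cut), with the lost degree of freedom included. Test size was 0.043–0.056 without the term and 0.043–0.059 with it. Mean estimates lay within 0.01 SD of the true zero in both.

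**The case against.** The strongest objection is that the diagram under the Moderation Models heading is not in the available text. In a path-model plan that is where the predictors of each outcome are drawn. If it shows the baseline outcome, only a mismatch between text and figure remains. The SAP is also terse, so item 4a may simply have lost a clause that the analyst will supply anyway. Both are possible. Neither can be settled from the text, and either way the written list needs correcting.

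The count is conditional: 18 needs moderator main effects, which item 4 does not name. The literal alternative is 21, so the condition does not enlarge the point.

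The size of the gain is assumed, and that stands in full. The low end for PAID is not a floor: lowering baseline-to-follow-up from 0.5 to 0.4 with the other inputs unchanged cuts the reduction to about 0.3%, roughly what the lost degree of freedom costs. The simulation shares these inputs, so it checks the algebra and the test size, not the size of the gain.

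The main comparisons in items 2 and 3 are untouched. The SAP already reports the final sample, so analysis may be under way or complete, and a change now could be post hoc. These points limit the weight of the concern without answering it.

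**Conclusion.** The concern holds for the SAP as written. Item 4a leaves out a covariate that item 3a treats as worth adjusting for, and nothing else in the readable text of item 4 supplies it for moderators 1 to 6. This affects 18 of 35 models at 6 months, and 12 of 28 at 3 months if those are run.

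The loss is one of precision only. Its size rests on assumed correlations and could be near zero. The balance still favours the change, because any partial correlation above 0.08 more than repays the degree of freedom. It is a should-fix point on secondary analyses. Confidence is medium because the diagram could not be seen.

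**What to change.** Extend item 4a with the baseline-outcome clause that closes item 3a, including its exception for TIR and QOL. All 35 models at 6 months would then contain the continuous baseline of their own outcome. State also that the condition and moderator main effects are fitted with every interaction. If the moderation diagram already shows the baseline term, bring the written list into line with it.

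The cost is one clause and a rerun of 18 models, plus 12 if 3-month models are run. No new data are needed. Each model loses one degree of freedom. Families without a baseline value need the same missing-data handling as in item 3. If outcomes have already been analysed, report the change as post hoc.
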